### Objectives for Day 4-7 post-CABG randomization

- To determine whether each of rivaroxaban 2.5 mg bid + aspirin 100 mg od and rivaroxaban 5 mg bid alone reduces the risk of bypass graft failure compared with aspirin 100 mg od
- To determine the association between post CABG graft failure and risk of a composite of myocardial infarction, stroke, or cardiovascular death in subjects with CAD or PAD

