#### 7.1.2.4 Follow-up visits

##### 7.1.2.4.1 Routine follow-up visits (Visits 3, 5, and 7-15+) - amended

Subjects will be seen in the clinic at Month 1 ( $\pm$  7 days), Month 6 ( $\pm$  4 weeks), and thereafter at 6 month intervals ( $\pm$  4 weeks) post-randomization until Visit 15. Thereafter, subjects will continue to be seen at the clinic every 6 months until the required number of primary efficacy outcomes has been collected. During the first year, subjects will be phoned at Month 3 and Month 9 to assess and encourage adherence to study treatments, and a further phone call (End of Washout Telephone Visit) will be made 30 days after the Final Follow-up Visit to assess outcomes and adverse events. Follow-up assessments include:

- Record outcomes
- Record adverse events (if appropriate, complete the Hospitalization CRF to allow collection of medical resource utilization [MRU] data)
- In patients randomized day 4-7 post CABG perform questionnaires (SAGE, DSS, MoCA, EQ-5D, Diet, and Physical Activity) (1 month).
- Collect blood sample for storage and central evaluation in COMPASS MIND substudy subjects at Visit 3 (1 month)
- Dispense study drug at Visits 5 and 7-15 by obtaining medication numbers through the PPD randomization and drug management system.
- Assess adherence to study drug
- Perform study drug accountability (pill count) at each in-clinic visit
- Perform CT angiography only at Visit 7 (1 year or later if not performed at 1 year) in all subjects who are randomized during the first week after CABG to evaluate graft patency (except in subjects with specific contraindications). In the event the subject undergoes an invasive coronary angiography at 1 year or later post CABG for any reason, a CT angiogram may not be required.

 “after randomization” was added as per Amendment 8. (See Section 13.2.2)

 Text added as per Amendments 6 and 8. (See Sections 13.1.2 and 13.2.2)

- Additional assessments to be performed only at Visit 9 (2 years) include:
  - Physical measurements: body weight (kg or lb), height (cm or in), waist circumference (cm or in), hip circumference (cm or in), heart rate (bpm), ankle-brachial blood pressure index (mm Hg)
  - Record concomitant medications
  - Administer diet and activity questionnaires at Visit 9
  - Administer MoCA, DSS, and SAGE questionnaires
  - Administer EQ-5D questionnaire

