### **8.3 Variables – amended**

Time (in days) from randomization to the first occurrence of

- the primary, secondary, tertiary efficacy outcomes (except SAGE, MoCA, DSS, and EQ5D, and MRU) for the antithrombotic treatment randomization (Sections [8.3.1](#), [8.3.2](#), [8.3.3](#)),
- the primary safety outcome for the antithrombotic treatment randomization (Section [8.3.4](#)), and
- the outcome for the pantoprazole randomization (Section [8.3.5](#))

will be analyzed as time-to-event variables.

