### 8.3.3 Tertiary and other efficacy outcomes - amended

The tertiary efficacy outcomes are:

- Subject-reported SAGE, MoCA, DSS, and EQ-5D
- Individual components of the primary and secondary outcomes
- Hospitalization for cardiovascular reasons
- Hospitalization
- Revascularization
- Amputation
- Stent thrombosis
- Unstable angina
- Worsening angina
- New angina
- Heart failure
- Venous thromboembolism^135
- Resuscitated cardiac arrest
- New diagnosis of cancer
- MRU
- Coronary artery bypass graft failure

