#### 8.4.1 Analysis of the primary efficacy outcome - amended

Analysis of the primary efficacy outcome will be based on the intention-to-treat principle (Section 8.2). Two comparisons will be performed to compare each of the rivaroxaban-based treatment groups to the common aspirin control group to evaluate:

- Superiority of rivaroxaban 2.5 mg bid + aspirin 100 mg od over rivaroxaban placebo + aspirin 100 mg od (control)

 Testing strategy text added as per Amendment 8. (See Section 13.2.2)

- Superiority of rivaroxaban 5 mg bid + aspirin placebo over rivaroxaban placebo + aspirin 100 mg od (control).

Each of the primary null hypotheses  $H_{0,riva2.5}$  and  $H_{0,riva5}$  stating that “there is no difference between the considered rivaroxaban-based treatment group and the aspirin control group in the probability of the primary efficacy outcome for all time points” will be tested against the respective alternative hypotheses  $H_{1,riva2.5}$  and  $H_{1,riva5}$  stating that “there is a difference between the two groups in the probability of the primary efficacy outcome for at least one time point”.

The 2 comparisons will be performed using 2 separate stratified log-rank tests. Following the mixture gatekeeping procedure as mentioned in Section 8.4, a truncated Hochberg test with the pre-specified truncation parameter  $\gamma = 0.9$  at  $\alpha=0.05$  will be used. Further details will be described in the SAP. PPI use (3 strata levels: not randomized to a PPI; pantoprazole 40 mg od; pantoprazole placebo) will be used as a stratification factor. Study center will not be used as a stratification factor. There will be no formal comparison between the rivaroxaban 2.5 mg bid + aspirin 100 mg od and rivaroxaban 5 mg bid + aspirin placebo groups.

Kaplan-Meier estimates of cumulative risk and cumulative hazard functions will be provided to evaluate the timing of event occurrence in the 3 antithrombotic study groups and the consistency of the respective treatment effects for all time points (the two survival curves in each comparison do not cross).

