Hazard ratio, relative risk reduction, and corresponding 2-sided 95% confidence intervals will be estimated based on 2 separate stratified Cox proportional hazards models. Censoring will be assumed independent of the randomized group assignment. The plausibility of the proportional hazards assumption will be assessed by visually examining both the plot of the log of the negative log of Kaplan-Meier estimates of the survival function versus the log of time for evidence of non-parallelism and the smoothed plot of the scaled Schoenfeld residuals to directly visualize the log hazard ratio, and by including a time-treatment interaction term in the Cox model (time log transformed). The significance of the interaction will be tested at the 5% type I error level. If the interaction is significant and there is strong evidence of non-proportionality from the plots, time-dependent hazard ratios will be estimated with the model that includes the interaction term. Further details will be specified in SAP.

The trial success will be determined based on the totality of evidence for significance, magnitude, and direction of treatment effect from the analysis of primary and secondary efficacy outcomes.

Analysis of the joint effect and/or interaction between rivaroxaban-based anti-thrombotic therapy and PPI use on the primary efficacy outcome will be performed as described in Section 8.4.5. Further details of this analysis will be specified in SAP.

---

 Paragraph was revised as per Amendment 8. (See Section 13.2.2)

 Text was deleted from this paragraph as per Amendment 8. (See Section 13.2.2)

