#### **8.4.3 Analysis of the tertiary efficacy outcomes**

Analysis of the tertiary efficacy outcomes will be based on the intention-to-treat principle (Section 8.2) and will use a similar approach as described in Section 8.4.1 (except for SAGE, MoCA, DSS, and EQ5D). Analysis of subject reported SAGE, MoCA, DSS, and EQ5D will be described in the SAP. Both comparisons of the rivaroxaban-based treatment groups to the common aspirin control group will be performed at the 2-sided 5% type I error level. Additional exploratory analyses will be conducted, as described in the SAP.

The MRU data will be incorporated into economic modeling, which will be performed and reported separately from this study.

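### Graft failure falls under time-to-first-occurrence with log-rank and Cox, although its recorded time is the date of detection, essentially that of one angiogram at one year or later

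*Protocol*

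**What the plan says.** Section 8.3 lists the outcomes whose time from randomization to first occurrence is the analysis variable: "the primary, secondary, tertiary efficacy outcomes (except SAGE, MoCA, DSS, and EQ5D, and MRU) for the antithrombotic treatment randomization". These "will be analyzed as time-to-event variables".

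Section 8.3.3 includes "Coronary artery bypass graft failure" among the tertiary outcomes. Section 8.4.3 says the tertiary analysis "will use a similar approach as described in Section 8.4.1 (except for SAGE, MoCA, DSS, and EQ5D", with each rivaroxaban arm compared with aspirin at the two-sided 5% level. Section 8.4.1 supplies the methods: "The 2 comparisons will be performed using 2 separate stratified log-rank tests", and hazard ratios "will be estimated based on 2 separate stratified Cox proportional hazards models".

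The outcome has its own objective in Section 2, for subjects randomized early after surgery: whether each rivaroxaban regimen "reduces the risk of bypass graft failure compared with aspirin 100 mg od".

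Ascertainment is described elsewhere:

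- Section 7.1.2.4.1: "Perform CT angiography only at Visit 7 (1 year or later if not performed at 1 year". No upper time limit is given.
- Section 4.1.1 waives the CT for specific contraindications (contrast allergy and low eGFR are the examples) and says it may not be needed if an invasive angiogram is done at about one year or later for any reason.
- Table 7–2, which applies after the early stop, attaches an outstanding one-year scan to the final rivaroxaban/aspirin visit.
- Section 7.5.3.1 also lists graft failure among the outcome events captured on the CRF.

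**The concern.** An angiogram shows whether a graft is blocked on the day of imaging. It does not show when the graft blocked. For most subjects the only time available to a log-rank test or Cox model is therefore a scheduling date, with an open upper limit and, after the early stop, a link to the calendar.

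Whether failure is seen at all depends on whether the subject was imaged. Imaging depends on events after randomization: survival, renal function, and angiography for other reasons. Section 8.4.1 assumes censoring independent of arm, and for this outcome that assumption carries much of the weight.

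At stake is the reading of one stated objective in about 2,000 subjects. A difference between arms in who is scanned, or when, can appear as a treatment effect on graft failure. Even with balanced scanning, the hazard ratio describes detection rather than occlusion.

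**Working it through.** **Is the method really fixed in the protocol?** Section 8.3 excepts SAGE, MoCA, DSS, EQ-5D and MRU. Section 8.4.3 excepts the four questionnaires and sets MRU aside for economic modelling. Graft failure is in neither list, and no other section gives it a different analysis. The method is therefore stated here and not left open for the SAP.

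**Is there a plan figure to reproduce?** No. The protocol gives no event count or power for graft failure, so the check is a simulation with no true treatment effect.

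**Inputs from the protocol**
- About 2,000 post-CABG subjects (Section 5), randomized 1:1:1: 2,000 / 3 ≈ 667 per arm.
- Failure probability 1/3 in both arms, from the background figure in Section 1.2.2 (1 in 3 patients with two or more grafts has a blocked graft at one year).
- Two-sided 5% per comparison (Section 8.4.3).

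**Assumptions, not in the protocol**
- Scan completion 75% to 90%, unrelated to graft status.
- Scan day normal with mean 380 and SD 20, shifted by 0 to 30 days in one arm. Follow-up ends between days 500 and 1,400.
- Event date = scan date.
- Two censoring rules, because Section 8.1 leaves censoring schemes to the SAP. Rule F: everyone without a detected failure is censored at final follow-up. Rule S: scanned subjects without failure are censored at the scan, unscanned subjects at one year.

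There were 3,000 runs per scenario. The comparator was a two-proportion z-test among scanned subjects.

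| Scenario, no true effect | Rule F: log-rank rejects (HR) | Rule S: log-rank rejects (HR) | Proportion among scanned rejects |
|---|---|---|---|
| 85% v 85%, same timing | 4.8% (1.00) | 5.1% (1.00) | 4.2–4.5% |
| 85% v 90% scanned | 10.3% (0.93) | 5.2% (0.99) | 5.1–5.3% |
| 80% v 90% scanned | 28.1% (0.87) | 6.3% (0.97) | 5.2–5.3% |
| 75% v 90% scanned | 52.8% (0.81) | 7.4% (0.95) | 4.7–5.0% |
| Scans 7 days later in one arm | 6.2% (0.97) | 85.5% (0.72) | 4.7–5.9% |
| Scans 14 days later | 9.1% (0.94) | 100% (0.51) | 5.0–5.1% |
| Scans 30 days later | 22.2% (0.89) | 100% (0.20) | 5.2–5.5% |

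**Hand check of the completion rows under rule F.** The detected proportion is completion × 1/3, and the rejection rate is approximately P(Z > 1.96 − d/SE) + P(Z < −1.96 − d/SE), where d is the difference in detected proportions and SE = √[p(1−p) × 2/667] at the mean proportion p.

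- 85% v 90%: 28.33% v 30.00%, d = 0.0167, SE = 0.0249, d/SE = 0.67, rejection ≈ 10%.
- 80% v 90%: 26.67% v 30.00%, d = 0.0333, SE = 0.0247, d/SE = 1.35, rejection ≈ 27%.

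Both agree with the simulation. Under rule F the test largely compares detected proportions over all randomized subjects, so unscanned subjects count as free of failure.

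**Why rule S behaves differently.** Each scanned subject leaves the risk set on the scan day, either as an event or as censored. The arm scanned later then has fewer events early in the scanning window, and the test picks up the calendar. Neither rule protects against both kinds of imbalance.

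**The case against.** **The censoring rule is not in the protocol.** This stands. Section 8.2.2 says which events count. Section 8.1 gives censoring schemes to the SAP. The 10% and 28% figures belong to rule F, and under rule S the same completion gaps give only 5–7%. Rule S is not an escape, however, because a 7-day timing shift then gives 85.5%.

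**Large imbalance is unlikely in a blinded trial.** This largely stands. Subjects and site staff are blinded (Section 6.5), and no section predicts a gap. The planning rates in Section 8.6 limit the part due to cardiovascular death: 3.3% per year × 20% ≈ 0.7 points per year for the whole primary composite, so less for deaths alone. Under rule F, 85% v 86% scanned gave 4.8% and 85% v 87% gave 5.6%. Mean scan delays of 67 v 60 days gave 5.3%, and 74 v 60 days gave 6.2%. Inflation under that rule needs a sizeable gap.

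**Section 8.4.7 handles unknown dates by taking a midpoint.** This does not repair the problem. With the event placed midway between surgery, or the Month 9 contact, and the scan, 80% v 90% completion still gave 25–28% false positives. The midpoint still depends on the scan date, and unscanned subjects still count as free of failure.

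**There is more than one detection route.** This is correct. Invasive angiography can replace the CT, and failures may be reported as CRF outcomes. That mixes scheduled with symptom-driven dates and does not turn them into occlusion dates.

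**Comparing proportions among scanned subjects also has a weakness.** This stands. It conditions on a post-randomization event and omits deaths. It held 4–6% here because missing scans were simulated as unrelated to patency.

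**Stronger readings that a reader might infer.** One is that everyone unscanned, including those who died, stays at risk to the Final Follow-up Visit. The protocol does not say so, and a dead subject has no such visit. Another is that the hazard ratio has no meaning, or that a 28% error rate is to be expected. Neither is supported: with balanced scanning the log-rank test holds about 5% and the simulated HR is 1.00.

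**Conclusion.** The point holds as a mismatch between a method the protocol states and data it describes. Graft failure is assigned to time-to-event analysis by omission from the exception lists, while its time is a detection date.

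The damage is conditional. With equal scan completion and timing the test keeps about 5%. With unequal completion it rises to about 10% (85% v 90%) or 28% (80% v 90%) if censoring is at final follow-up. With unequal timing it rises severely if censoring is at the scan. These figures rest on assumed completion, timing and censoring rules, and the protocol gives none of the three.

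The outcome is tertiary, lies outside the gatekeeping families in Section 8.4, and concerns about 2,000 of 27,400 subjects. No primary or secondary conclusion depends on it. It should still be corrected, because it answers a stated objective for which those subjects undergo a protocol angiogram.

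**What to change.** Add graft failure to the exceptions in Sections 8.3 and 8.4.3. Then state that:

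- it is analysed as a binary outcome, any failed graft per subject at the scan, among assessed subjects, for each rivaroxaban arm against aspirin, stratified by the three PPI strata of Section 8.4.1;
- scan completion and time from surgery to scan are reported by arm;
- a sensitivity analysis covers unscanned subjects and deaths, because the assessed-only comparison assumes that missing scans are unrelated to patency.

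The choice of model can stay with the SAP. The cost is a few sentences and one extra table, with no new data collection.

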#### **8.3.1 Primary efficacy outcome**

The primary efficacy outcome is the composite of the following outcomes:

- Myocardial infarction
- Stroke
- Cardiovascular death

#### **8.3.2 Secondary efficacy outcomes - amended**

The secondary efficacy outcomes are (in the following order):

- The composite of outcomes --- coronary heart disease death, myocardial infarction, ischemic stroke, acute limb ischemia
- The composite of outcomes --- cardiovascular death, myocardial infarction, ischemic stroke, acute limb ischemia

---

 Text modified/added as per Amendments 6 and 8. (See Sections [13.1.2](#) and [13.2.2](#))

- Mortality (all-cause)

### 8.3.3 Tertiary and other efficacy outcomes - amended

The tertiary efficacy outcomes are:

- Subject-reported SAGE, MoCA, DSS, and EQ-5D
- Individual components of the primary and secondary outcomes
- Hospitalization for cardiovascular reasons
- Hospitalization
- Revascularization
- Amputation
- Stent thrombosis
- Unstable angina
- Worsening angina
- New angina
- Heart failure
- Venous thromboembolism^135
- Resuscitated cardiac arrest
- New diagnosis of cancer
- MRU
- Coronary artery bypass graft failure

### 8.3.4 Primary safety outcome

The primary safety outcome is modified ISTH major bleeding, defined as:

- fatal bleeding, and/or
- symptomatic bleeding in a critical area or organ, such as intracranial, intraspinal, intraocular, retroperitoneal, intraarticular or pericardial, or intramuscular with compartment syndrome, or bleeding into the surgical site requiring reoperation, and/or
- bleeding leading to hospitalization

### 8.3.5 Outcome for pantoprazole randomization - amended

The outcome for the pantoprazole randomization is the composite of the following outcomes:

- Overt bleeding of gastroduodenal origin confirmed by endoscopy or radiography
- Overt upper gastrointestinal bleeding of unknown origin

---

 Added as per Amendment 8. (See Section 13.2.2)

 Text deleted as per Amendment 6. (See Section 13.1.2)

 Text modified as per Amendment 6. (See Section 13.1.2)

- Bleeding of presumed occult gastrointestinal origin with documented decrease in Hb of 2 g/dL
- Symptomatic gastroduodenal ulcer
- Gastrointestinal pain with underlying multiple gastroduodenal erosions, obstruction or perforation

### 8.3.6 Subgroup variables - amended

Homogeneity of treatment effect will be examined for the following subgroup variables:

- CAD (yes, no)
- PAD (yes, no)
- CAD and PAD (yes, no)
- CAD only, PAD only, CAD and PAD
- CABG days 4-7 before randomization (yes, no)
- Any prior CABG (yes, no), further subdivided as CABG days 4-7 before randomization and other prior CABG
- Region (North America, Western Europe, Eastern Europe, Asia Pacific and other, and South America)
- History of a prior heart failure (yes, no)
- History of non-lacunar ischemic stroke  $\geq 1$  months ago (yes, no)
- Sex (male, female)
- Age (<55, 55 - <65, 65 - 75, >75 years)
- Race (White or Caucasian, Black or African American, Asian, other)
- Baseline renal function (estimated glomerular filtration rate <60,  $\geq 60$  mL/min)
- Baseline diabetes (yes, no)
- Smoking status at baseline (smoker, nonsmoker)
- Baseline PPI use (yes, no)

Additional subgroup variables, if identified, will be specified in the SAP prior to unblinding of the treatment assignment.

## 8.4 Statistical and analytical plans - amended

Summaries by randomized group using appropriate descriptive statistics will be provided for all study variables including demographic and baseline characteristics. Mean, median, standard deviation, minimum, and maximum will be used to summarize continuous variables. Counts and percentages will be used to summarize categorical variables.

### Testing strategy

---

 Text deleted as per Amendment 6. (See Section 13.1.2)

 Bullet was added as per Amendment 8. (See Section 13.2.2)

Each of the rivaroxaban-based treatment groups will first be compared to the common aspirin control group on the primary efficacy outcome, followed by the same comparisons on the three ordered secondary efficacy outcomes. Figure 8–1 illustrates the hypothesis testing problem with ordered hypotheses. The null hypotheses of no effect corresponding to different efficacy outcomes will be grouped into four separate families. Standard logical restrictions will be imposed, i.e., the null hypotheses will be split into two branches corresponding to the tests for rivaroxaban 2.5 mg plus aspirin (hypotheses  $H_{1A}$ ,  $H_{2A}$ ,  $H_{3A}$ ,  $H_{4A}$ ) and to the tests for rivaroxaban 5.0 mg (hypotheses  $H_{1B}$ ,  $H_{2B}$ ,  $H_{3B}$ ,  $H_{4B}$ ). A null hypothesis within each branch can be tested if and only if the immediately preceding null hypothesis is rejected, e.g., hypothesis  $H_{2A}$ , is “testable” if and only if hypothesis  $H_{1A}$  is rejected. In Figure 8–1, these logical restrictions are represented by arrows.

[figure not shown]

Figure 8–1: Hypothesis testing problem

Multiple hypotheses testing will be performed according to a mixture gatekeeping procedure based on the Hochberg test with a truncation fraction of  $\gamma = 0.9$ , which controls the familywise error rate at the pre-assigned level of significance  $\alpha = 5\%$  in the strong sense. The Hochberg-based gatekeeping procedure based on an extension of the general mixture methodology developed in Dmitrienko and Tamhane (33,34) was recently proposed in Brechenmacher et al. (32) Details for the setting of this study will be described in the SAP.

#### 8.4.1 Analysis of the primary efficacy outcome - amended

Analysis of the primary efficacy outcome will be based on the intention-to-treat principle (Section 8.2). Two comparisons will be performed to compare each of the rivaroxaban-based treatment groups to the common aspirin control group to evaluate:

- Superiority of rivaroxaban 2.5 mg bid + aspirin 100 mg od over rivaroxaban placebo + aspirin 100 mg od (control)

 Testing strategy text added as per Amendment 8. (See Section 13.2.2)

- Superiority of rivaroxaban 5 mg bid + aspirin placebo over rivaroxaban placebo + aspirin 100 mg od (control).

Each of the primary null hypotheses  $H_{0,riva2.5}$  and  $H_{0,riva5}$  stating that “there is no difference between the considered rivaroxaban-based treatment group and the aspirin control group in the probability of the primary efficacy outcome for all time points” will be tested against the respective alternative hypotheses  $H_{1,riva2.5}$  and  $H_{1,riva5}$  stating that “there is a difference between the two groups in the probability of the primary efficacy outcome for at least one time point”.

The 2 comparisons will be performed using 2 separate stratified log-rank tests. Following the mixture gatekeeping procedure as mentioned in Section 8.4, a truncated Hochberg test with the pre-specified truncation parameter  $\gamma = 0.9$  at  $\alpha=0.05$  will be used. Further details will be described in the SAP. PPI use (3 strata levels: not randomized to a PPI; pantoprazole 40 mg od; pantoprazole placebo) will be used as a stratification factor. Study center will not be used as a stratification factor. There will be no formal comparison between the rivaroxaban 2.5 mg bid + aspirin 100 mg od and rivaroxaban 5 mg bid + aspirin placebo groups.

Kaplan-Meier estimates of cumulative risk and cumulative hazard functions will be provided to evaluate the timing of event occurrence in the 3 antithrombotic study groups and the consistency of the respective treatment effects for all time points (the two survival curves in each comparison do not cross).

Hazard ratio, relative risk reduction, and corresponding 2-sided 95% confidence intervals will be estimated based on 2 separate stratified Cox proportional hazards models. Censoring will be assumed independent of the randomized group assignment. The plausibility of the proportional hazards assumption will be assessed by visually examining both the plot of the log of the negative log of Kaplan-Meier estimates of the survival function versus the log of time for evidence of non-parallelism and the smoothed plot of the scaled Schoenfeld residuals to directly visualize the log hazard ratio, and by including a time-treatment interaction term in the Cox model (time log transformed). The significance of the interaction will be tested at the 5% type I error level. If the interaction is significant and there is strong evidence of non-proportionality from the plots, time-dependent hazard ratios will be estimated with the model that includes the interaction term. Further details will be specified in SAP.

The trial success will be determined based on the totality of evidence for significance, magnitude, and direction of treatment effect from the analysis of primary and secondary efficacy outcomes.

Analysis of the joint effect and/or interaction between rivaroxaban-based anti-thrombotic therapy and PPI use on the primary efficacy outcome will be performed as described in Section 8.4.5. Further details of this analysis will be specified in SAP.

---

 Paragraph was revised as per Amendment 8. (See Section 13.2.2)

 Text was deleted from this paragraph as per Amendment 8. (See Section 13.2.2)

